## 6.5. Missing Data

For the primary endpoint of incidence of mechanical ventilation or death, subjects who are lost to follow-up before Day 29 prior to having an event and have their last assessment within window for Day 29 (i.e., Day 26, 27, 28) will be considered as non-events by Day 29 regardless of their discharge status at that time.

Remaining missing data for subjects lost to follow-up after discharge, while still hospitalized, or with no post baseline data will be imputed using multiple imputation. The main sensitivity analysis will consider subjects missing data while discharged as non-events and use a similar multiple imputation as the primary analysis for remaining missingness. Additional sensitivity analyses of the primary endpoint will use the same imputation approach as the primary analysis on different analysis populations and using different covariates in the final model.

Two secondary analyses of the primary endpoint will be conducted: the first is based on targeted maximum likelihood estimation (TMLE), and the second is a multiple imputation approach that uses TMLE for analysis of each imputed dataset. These approaches are described in Section 6.5.2.

Analysis of time to event endpoints (i.e., sustained recovery, time to improvement, time to mechanical ventilation or death) will be based on observed ordinal score along with discharge and death information. Refer to Table 2 for additional details regarding censoring and handling of missing data for all endpoints.

Some analyses of ordinal score such as ordinal scores over time described in Section 6.5.1 of the master SAP will be performed based on the complete dataset of ordinal score created using the following steps:

- All planned timepoints after death are assigned a score of 8
- Intermittent missingness:
  - Impute the intermittent missing ordinal score as 1 if the scores reported before and after the missing value are both 1 and no change in oxygen use or hospitalization status after discharge to a location other than hospice, long term acute care or other hospital.
  - Impute the intermittent missing ordinal score as 2 after discharge to a location other than hospice, long term acute care or other hospital if the subject doesn't fall into the category above and subject is not hospitalized at the time point.
  - Remaining intermittently missing data imputed using last observation carried forward.

- All remaining missing ordinal scores after last assessment imputed using last observation carried forward.

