8.1.2.1 Measures of Clinical Support, Limitations and Infection Control

The subject's clinical status will be captured on each study day while hospitalized up until and including Day 29. Once subjects are discharged from the hospital, they will have a study visit on Days 8, 15, 22, 29, and 60 visits (only the ordinal score will be obtained on Day 60) as an outpatient. The Day 8, Day 22 and Day 60 visits do not have laboratory tests or collection of samples and may be conducted by phone. Day 15 and 29 visits are preferred to be in person in order to collect safety laboratory testing, stored samples, and virologic assessments but may be performed by phone. Clinical status is largely measured by the ordinal scale. The ordinal scale can also be evaluated over the phone if the discharged subject is unable to return for in-person visits on Day 15 and 29.

Ideally, the ordinal scale is completed concurrently with the NEW Score just prior to study product administration. The following measures are recorded for the ordinal scale. See MOP for more detailed description of ventilatory devices in each category:

- Hospitalization.
- Oxygen requirement.
- Non-invasive mechanical ventilation (via mask) requirement.
- High-flow oxygen requirement.
- Invasive mechanical ventilation (via endotracheal tube or tracheostomy tube) requirement.
- ECMO requirement.
- Ongoing medical care preventing hospital discharge (COVID-19 related or other medical conditions).
- Limitations of physical activity (self-assessed and reported as new or increased limitations as compared to status prior to the onset of COVID-19)).
- Isolated for infection control purposes.

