## Appendix 6 BET-B

Endpoint	Analysis	Imputation/Censoring Method
mg/L.	Sensitivity	
 
Use the complete data for ordinal score to define survival without respiratory failure.
 
Subjects whose last assessment in the study is before Day 29 and were discharged to a location other than LTAC, hospice care or other hospital, or progressed to mechanical ventilation or death after Day 29 will be considered non-events and censored at Day 29.
 
Subjects whose last assessment in the study is before Day 29 and before progression to mechanical ventilation or death and without being discharged to a location other than LTAC, hospice care or other hospital at their last assessment will be considered non-events and censored at the date of their last observed assessment.
 
Subjects who complete follow-up without mechanical ventilation or death will be censored at the expected study Day 29.
 

Time to Sustained Recovery up to Day 60 in subjects who are < 85 years old, have baseline clinical status of 5 or 6, and baseline CRP < 150 mg/L.	Primary and subgroup	
 
Use the complete data for ordinal score to derive sustained recovery.
 
Subjects whose last assessment in the study is prior to Day 60 prior to recovery will be considered not recovered and censored at the date of last follow-up.
 
Death prior to recovery will be considered not recovered and censored at expected study Day 60.
 

	Sensitivity	
 
Use the complete data for ordinal score to derive sustained recovery.
 
Subjects whose last assessment in the study is prior to Day 60 after discharge from the hospital to a location other than LTAC, hospice care or other hospital will be treated as recovered by Day 60. Their time to recovery will be the day the time of their first observed/imputed recovery score (i.e; 1, 2, 3) or the day of discharge, whichever comes first.
 
Subjects whose last assessment in the study is prior to Day 60 without being discharged from the hospital to a location other than LTAC, Hospice care or other hospital at their last assessment will be considered not recovered and censored at the date of last follow-up.
 
Death prior to recovery will be considered not recovered and censored at expected study Day 60.
 

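### In the SAP 6.5 completed ordinal-score dataset, a subject discharged home with no later score keeps the last in-hospital score to Day 29 and is counted as hospitalised, unlike under the SAP's own rule for intermittent gaps.

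*SAP*

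**What the plan says.** SAP 6.5 (Missing Data) builds a completed set of ordinal scores. Its scope is given as "Some analyses of ordinal score such as ordinal scores over time described in Section 6.5.1 of the master SAP". Planned timepoints after death are scored 8. Two further steps matter here.

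- **Intermittent gaps.** If the scores on both sides of the gap are 1, and oxygen use and hospital status have not changed since a home discharge, the gap is filled with 1. Otherwise the rule is: "Impute the intermittent missing ordinal score as 2 after discharge to a location other than hospice, long term acute care or other hospital", provided the subject is not in hospital at that timepoint. Any other intermittent gap takes the last observed score.
- **Gaps after the last assessment.** "All remaining missing ordinal scores after last assessment imputed using last observation carried forward". Discharge is not mentioned.

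On timing, Protocol 8.1.2.1 says that "clinical status will be captured on each study day while hospitalized up until and including Day 29". Of discharged subjects it says "they will have a study visit on Days 8, 15, 22, 29, and 60 visits", and phone contact is allowed. Protocol Table 4 defines scores 1 and 2 as not hospitalised and score 3 as hospitalised.

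Two statements on time-to-event endpoints do not sit easily together. SAP 6.5 says these analyses "will be based on observed ordinal score along with discharge and death information". SAP Table 2 says, for recovery: "Use the complete data for ordinal score to derive sustained recovery".

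**The concern.** The two steps treat the same fact differently. When a later score exists, the SAP uses the recorded discharge and assigns 2. When no later score exists, it ignores the discharge and repeats the last ward score. A carried-forward 3 or higher is then not a cautious guess about an unknown state, because it conflicts with a recorded one.

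The route to this is ordinary. Scores are taken daily on the ward and, ideally, just before dosing, so the last score before leaving can be an in-hospital one. The next score is due at the first outpatient contact. Protocol 1.1.1 reports that about 75% of each arm of the earlier phase 3 trial's subgroup had been discharged by Day 8, so leaving before that contact may be common. How many such subjects are then never reached is not stated.

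At stake are descriptions of clinical status over time and, possibly, comparisons at fixed days. If loss after discharge, or the last ward score, differs by arm, part of that difference would appear as a difference in hospitalisation.

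**Working it through.** The plan gives no figure on this point to reproduce. SAP 5 says only that little missing data are expected.

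**Step 1: apply the SAP 6.5 steps literally.** Take a subject sent home on Day 5, alive and not readmitted.

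| What is recorded | Day 8 | Day 15 | Day 22 | Day 29 |
|---|---|---|---|---|
| Last ward score 5, no later score | 5 | 5 | 5 | 5 |
| Last ward score 4, no later score | 4 | 4 | 4 | 4 |
| Last ward score 3, no later score | 3 | 3 | 3 | 3 |
| Last ward score 5, Day 8 score 2, then lost | 2 | 2 | 2 | 2 |
| Last ward score 5, Day 8 missed, Day 15 score 1, then lost | 2 | 1 | 1 | 1 |
| Last ward score 5, score 2 recorded on the day of discharge, then lost | 2 | 2 | 2 | 2 |
| Last ward score 5, Days 8 to 29 missed, reached on Day 60 | 2 | 2 | 2 | 2 |

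Only the first three rows are wrong. In the last row the Day 60 score makes the earlier gaps intermittent, so the score-2 rule covers them. The error therefore needs no score at any contact after discharge, Day 60 included.

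**Step 2: which analyses are touched.**

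- Primary endpoint: not touched. SAP 6.5 and 6.5.1 use multiple imputation, with a separate group for subjects lost after discharge home.
- Ordinal scores over time: touched, since SAP 6.5 names them.
- Clinical status at Days 8, 15 and 29 and mean change in score (Protocol Table 4, other secondary): plausible but not confirmed. SAP Table 2 sends the reader to the master SAP for the imputation methods of these endpoints.
- Time to ventilation or death: a carried-forward 3 to 6 is not an event, so the rule cannot create one.
- Time to sustained recovery: unclear. SAP 8.2.2 counts discharge home as recovery, and SAP 6.5 and Table 2 differ on whether observed or completed scores are used.

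**Step 3: size.** Let f be the share of an arm that is affected (an assumption) and s the last ward score. Measured against score 2, the SAP's own value for intermittent gaps:

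overstatement of the arm's Day 29 mean = f × (s − 2)

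The share wrongly counted as hospitalised is f. The planned arm size is 275 (Protocol 5, SAP 4.3).

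| f (assumed) | Subjects, f × 275 | s = 3 | s = 4 | s = 5 |
|---|---|---|---|---|
| 1% | 2.75 | 0.01 | 0.02 | 0.03 |
| 2% | 5.5 | 0.02 | 0.04 | 0.06 |
| 4% | 11 | 0.04 | 0.08 | 0.12 |

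**Step 4: between arms.** The bias in the mean difference is f₁ × (s₁ − 2) − f₂ × (s₂ − 2). With equal loss and equal last scores it is 0. With an assumed 4% against 1% and equal last scores it is (0.04 − 0.01) × (s − 2), that is 0.03 to 0.09 for s from 3 to 5. The spurious difference in hospitalisation is then 4 − 1 = 3 percentage points.

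**The case against.** The best reply is that this is a small matter. An affected subject must miss every scheduled contact through Day 60, although a phone call suffices. For a discharge on Day 6, the Day 8 visit with its window of 2 days either side falls due within about four days. The SAP expects little missing data. The endpoints likely to be affected are outside the testing hierarchy (Protocol 9.2.4, SAP 6.8), and equal loss in both arms largely cancels in a comparison. All of that stands and limits the importance of the point. It does not make the assigned score correct.

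A reader might infer more than the documents support:

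- That everyone discharged home and then lost is affected. One post-discharge score prevents the error, as Step 1 shows.
- That these subjects would often be shown as on oxygen. No distribution of last ward scores is given; the last score could be 3, 4, 5 or 6.
- That all ordinal-score endpoints are built on this dataset. SAP 6.5 limits it to some analyses, and the master SAP was not supplied.
- That the recovery sensitivity analysis in SAP 8.2.2, which counts such subjects as recovered, contradicts this rule. It is a deliberately different assumption for a different endpoint. The inconsistency lies between the two gap rules inside SAP 6.5.

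**Conclusion.** The point holds in this limited form. As written, SAP 6.5 gives a wrong value, not merely an incomplete instruction, for subjects sent home who have no ordinal score afterwards: they remain hospitalised in the completed dataset to Day 29. If the discharge rule was meant to cover these gaps as well, the text does not say so, and a programmer following it would carry the ward score forward.

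The size cannot be fixed from the documents. It is f × (s − 2) on an arm's Day 29 mean and f on the share counted as hospitalised, with both f and s assumed. A bias between arms arises only if loss or last scores differ by arm. No confirmatory conclusion is shown to change. The point is worth correcting because the error is plain and the remedy is cheap.

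**What to change.** Replace the sentence on gaps after the last assessment in SAP 6.5 with:

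> After the last assessment, a subject whose last known status is discharge home (any destination except hospice, LTAC or another hospital) is given score 2, or score 1 if the last score recorded after discharge was 1. For all other subjects the last observed score is carried forward.

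Keep plain carry-forward for everyone as a sensitivity analysis. State in SAP 6.5 which endpoints use the completed dataset, and reconcile the observed-score wording there with the complete-data wording in SAP Table 2.

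The main change costs one sentence and one programming condition. Discharge destination is already collected and is used in SAP 6.5.1.2, so no new data are needed. The sensitivity analysis is one further run of the same programs.

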### 6.5.1. Multiple Imputation

The multiple imputation approach will classify subjects with missing event into 3 categories as listed below and will apply different imputation models for each as detailed in this section.

#### 6.5.1.1. Imputation Strategy for Subjects Lost to Follow-up with no Post-Baseline Data

This group includes subjects randomized but who withdrew from the study soon after randomization without any post-baseline data. Missing incidence of mechanical ventilation or death data for these subjects will be imputed using multiple imputation model implemented using PROC MI procedure in SAS based on the monotone logistic regression model. The imputation model will include the following covariates: Randomized treatment group (trtvar), baseline dexamethasone use (basedexafl), actual baseline ordinal score (baseordscorevar), age, indicator for black or Hispanic ethnicity (blackhispfl), presence of 2 or more comorbidities (comorb2fl), and baseline CRP (basecrp).

Since missing data in any of these baseline characteristics may cause issues with the monotone missing data patterns, the following methods will be used to fill in missing baseline covariates data:

- For continuous baseline covariates (age, CRP), mean imputation will be used to replace missing values with the overall mean value from all randomized subjects for the given covariate. Note that there will not be any missing data for age and baseline CRP for subjects in the primary subgroup, but there will be some missingness in either of these variables for some of the subjects in the full ITT population.
- For indicator variables of baseline dexamethasone use, black or Hispanic ethnicity, presence or two or more comorbidities, subjects with missing values will be given the value with the greatest number of subjects among all randomized subjects.
- We do not anticipate any missing data for actual baseline ordinal score.

In the case that more than 1% of subjects have missing baseline covariates and the overall p-value for the primary endpoint is  $< 0.1$ , a sensitivity analysis will be performed that uses a fully conditional specification (FCS) to impute missing baseline covariates. This is implemented by replacing the `monotone logistic` line in the PROC MI pseudocode shown below with the following line:

```
fcs logistic(eventD29= trtvar baseordscorevar basedexausevar age blackhispfl comorb2fl
basecrp );
```

For most of the modeling, the reference group for categorical variables will be 'No' for indicator variables, 'Placebo + RDV' for treatment group, and '6 or 7' for actual baseline ordinal score. As an exception, analyses based on the primary subgroup will use ordinal score '6' as the reference group for actual baseline ordinal score.

#### Pseudocode:

- DEFINE eventD29 as the binary variable for death or progression to mechanical ventilation or death by Day 29 (1=Yes, 0=No, .=Missing)
- DEFINE input1 as the full analysis dataset containing all baseline covariates and event indicator for complete data subjects as well as subjects with no post-baseline data with missing event indicator to be imputed.

- DEFINE imp\_out1 as the output dataset containing the 20 imputed datasets

```
proc mi data=input1  out= imp_out1 nimpute=20 seed = 837405 nointprint;
class trtvar baseordscorevar basedexausefl blackhispfl comorb2fl eventD29;
var trtvar baseordscorevar basedexausefl age blackhispfl comorb2fl basecrp eventD29;
monotone logistic(eventD29= trtvar baseordscorevar basedexausevar age blackhispfl
comorb2fl basecrp );
run;
```

The above procedure will output imp\_out1 dataset which contains 20 replicates for each subject. Update the dataset to remove subjects with complete data and only keep the 20 imputed datasets for subjects with no post-baseline data.

#### 6.5.1.2. Imputation Strategy for Subjects Lost to Follow-up while Discharged

This group includes subjects with post-baseline data available who were lost to follow-up or terminated early from the study prior to Day 29 and prior to death or progression to mechanical ventilation and were discharged to a location other than LTAC, hospice care or other hospital at the time of their last assessment.

##### Imputation Approach if Less than 10 Events are Observed

If, as expected, less than 10 post-discharge events are observed in the discharged group, missing incidence of mechanical ventilation or death data for these subjects will be imputed from a simple binomial distribution with the event rate calculated as the proportion of discharged subjects with known outcome (i.e., discharged to a location other than LTAC, hospice care or other hospital) who died or progressed to mechanical ventilation after discharge, without adjusting for any covariates in this group.

If no event is observed in a given analysis such as in subgroup analyses, the event rate of 0.5/total number of discharged subjects with outcome in the subgroup will be used instead of 0.

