### **4.3. Selection of Study Population**

Approximately 550 (275 Lenzilumab + RDV and 275 shared placebo) male and non-pregnant female adults  $\geq 18$  years of age or older with COVID-19 and who meet all eligibility criteria will be enrolled at up to 70 domestic sites and 5 international sites. The target population should reflect the community at large. The estimated time from screening (Day -1 or Day 1) to end of study for an individual subject is approximately 60 days.

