## 5. SAMPLE SIZE CONSIDERATIONS

The LIVE-AIR trial estimated a HR of about 1.5 in its overall population, and a HR of above 3 in the identified subgroup. The corresponding relative risks for the primary endpoint were in the 2.5 or 2.6 range, and the corresponding odds ratios were around 3. Because the treatment effect in the post hoc subgroup may be overly optimistic, the BET-B updated sample size assumes an intermediate odds ratio of 2.5 for the subgroup. The LIVE-AIR trial also observed a 21% event rate in the placebo group in the subgroup, which is likely higher than expected in this trial.

A sample size of 400 in the subgroup will yield 80% power if the control event rate is 16% and 89% power if the control rate is 21%, if the odds ratio is 2.5 and a two-sided alpha=.049. (An odds ratio of 2.5 is defined such that if the control event rate is 16%, the treated rate would be 7%.) At most 550 participants (that is, subjects randomized into BET-B and relevant shared controls) will be randomized. Based on early BET baseline estimates, roughly 75% of subjects are expected to fall in the primary analysis subgroup at baseline (CRP<150mg/L, age<85, and baseline ordinal score < 7). The trial will enroll subjects until 400 are randomized in the subgroup or 550 overall, whatever comes first. These calculations are not inflated for missing data, as little missing data are expected.

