**Pe = Prob (Event by Day 29|no event through last assessment) = 1 – S29/SL**

**Step 4:** For each subject lost to follow-up while discharged or transferred to another hospital, impute the event from a binomial distribution using the event probability calculated in Step 3.

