#### Odds ratios from logistic regression using multiple imputation:

```
proc logistic data=imp_out out=imp_parms;
  by _imputation_;
  class baseordscorevar (param=ref ref=5) basedexausevar (param=ref ref=no steroid
use) trtvar (param=ref ref=placebolabel);
  model eventd29 (eventd29='1') = trtvar baseordscorevar basedexausevar age
baseCRP;
  ods output oddsratioswald = orest parameterestimates=pars;
run;

*Keep only estimates for the treatment variable;
data pars1;set pars;where Variable='Treatment variable';run;
*Combine estimates;
PROC MIANALYZE DATA=pars1;
  ODS OUTPUT PARAMETERESTIMATES= logor;
  MODELEFFECTS estimate ;
  STDERR stderr ;
RUN;
*Transform estimates from the log(OR) scale to the OR scale;
data OR;
  SET logor;
  OR_estimate = EXP(ESTIMATE);
```

```

OR_LCL_95 =OR_estimate*EXP (-1.96*STDERR) ;
OR_UCL_95 =OR_estimate*EXP (+1.96*STDERR) ;
OR_LCL_80 =OR_estimate*EXP (-1.28*STDERR) ;
OR_UCL_80 =OR_estimate*EXP (+1.28*STDERR) ;

RUN;run;
    
```

To estimate risk differences from logistic regression, the approach from Ge et. al [1] as described below:

```

proc logistic data = dataset outmodel=pout;
    class trtvar ;
    model surv(event='1') = trtvar othercovariates ;
run;

*Create dataset tempa to contain all subjects and assign them the active Lenzilumab + RDV and dataset tempb which include all subjects assigned the placebo treatment;

proc logistic inmodel=pout;
    score data = tempa out=preda(keep=id P_a rename= (P_1=P_a)) ;
run;

proc logistic inmodel=pout;
    score data = tempb out=predp(keep=id P_1 rename= (P_1=P_p)) ;
run;

proc sort data=preda;by subjectid;run;
proc sort data=predp;by subjectid;run;

*Combine to obtain risk differences in probabilities for each subject;

data comb;
    merge predp preda;
    by subjectid;
    diff=P_a-P_p;
run;

proc means data=comb; var diff; run;
    
```

To obtain the CI for the risk difference, use bootstrap with the following steps:

1. Sample with replacement from the dataset.
2. Obtain risk difference estimate for each bootstrap sample.
3. Repeat this step the above step 1000 times and use the 2.5th and 97.5th percentiles of the risk estimates as the limits for the 95% CI for the risk difference. The risk difference from bootstrap should be equal to the risk difference obtained prior to performing bootstrap.

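### The primary multiple imputation holds some event probabilities fixed over all 20 imputations, so the pooled standard error leaves out their uncertainty; the effect is very small

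*SAP*

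**What the plan says.** SAP 8.1.1 makes multiple imputation the method for missing primary outcomes, and SAP 6.5.1 splits the missing subjects into three groups.

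- **No post-baseline data (6.5.1.1).** PROC MI with a monotone logistic model, which draws new regression parameters for each imputation.
- **Lost after discharge (6.5.1.2).** With fewer than 10 post-discharge events, the branch the SAP expects, the missing outcome "will be imputed from a simple binomial distribution with the event rate calculated as the proportion of discharged subjects" with a known outcome who had the event. The code sets this rate once, before the loop over 20 imputations. With 10 or more events the SAP switches to PROC MI with baseline ordinal score as covariate.
- **Lost while hospitalised or after transfer (6.5.1.3).** One Cox model gives each subject Pe = 1 - S29/SL. Step 4 is then to "impute the event from a binomial distribution using the event probability calculated in Step 3". The code again sets the probability before the loop. Step 4 names the group as discharged or transferred, but the section title and Step 3 show that hospitalised or transferred is meant.

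The 20 treatment estimates are pooled with "PROC MIANALYZE DATA=pars1". The risk-difference interval comes from a bootstrap run inside datasets that are already imputed, so it does not re-estimate these probabilities either.

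**The concern.** Rubin's rules give a valid variance when each imputation reflects two sources of uncertainty: the random outcome given the model, and the estimation error in the model. With a fixed probability the 20 datasets differ only by binomial noise, and the second source is lost. The between-imputation variance is then too small and the interval for the primary odds ratio too narrow.

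The plan is also uneven. Parameter uncertainty is carried for subjects with no post-baseline data and for 10 or more post-discharge events. It is dropped in the sparse branch, where the rate is least certain. For illustration, 3 events in 250 known outcomes give 1.2%, with a Jeffreys interval of 0.3% to 3.2%. At stake is the precision claimed for the primary result of a trial that SAP 3.1 describes as confirmatory.

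**Working it through.** **Inputs from the documents.** SAP 5 gives 400 subjects in the subgroup and "89% power if the control rate is 21%, if the odds ratio is 2.5"; at a 16% control rate it gives 80% power and a treated rate of 7%, at two-sided alpha 0.049. SAP 4.3 gives "275 Lenzilumab + RDV and 275 shared placebo", so 1:1 and 200 per arm in the subgroup. There are 20 imputations. No missing-data rate is given beyond the statement that little is expected.

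**The plan's own figure.** An odds ratio of 2.5 at 16% gives treated odds (0.16/0.84)/2.5 = 0.0762, so a rate of 7.08%. The unpooled standard error is √(0.16×0.84/200 + 0.0708×0.9292/200) = 0.0316, and z = 0.0892/0.0316 = 2.82. Power is Φ(2.82 - 1.969) = 80.3%. At 21% the treated rate is 9.61%, z = 3.20 and power is 89.2%. Both match the SAP, so these rates are a sound basis for the check.

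**Variance formula.** Rubin's total variance is T = W + (1 + 1/20)B, where W is the within-imputation and B the between-imputation variance. The omission acts mainly through B.

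**Simulation with a treatment-only Cox model.** 800 trials per scenario, 16% vs 7.08%. The fixed probabilities of the SAP were compared with a Beta-drawn discharged rate plus a Cox model refitted on a bootstrap sample in each imputation. Assumed: post-discharge event rate 1.5%, about 90% of subjects without an in-hospital event discharged, nobody in the no-post-baseline group.

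| Missing | W | B fixed | B redrawn | B shortfall | SE fixed | SE redrawn |
|---|---|---|---|---|---|---|
| 6% | 0.1186 | 0.0024 | 0.0026 | 8% | 0.3464 | 0.3464 |
| 17% | 0.1240 | 0.0097 | 0.0104 | 7% | 0.3645 | 0.3651 |
| 33% | 0.1327 | 0.0196 | 0.0220 | 11% | 0.3884 | 0.3910 |

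The shortfall in B is 1 - fixed/redrawn, for example 1 - 0.0196/0.0220 = 11%. It barely reaches the SE because W dominates: B/W is 0.0024/0.1186 = 2% at 6% missing and 0.0196/0.1327 = 15% at 33%. The ratio of SEs (redrawn over fixed), including null runs at 11.5% in both arms, was 1.000 at 6%, 1.000-1.001 at 13%, 1.002-1.004 at 17% and 1.006-1.007 at 33%.

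The discharged step alone matters least. With 16% discharged losses and no hospitalised losses the ratio was 1.0008 (1.0002 under the null). One rate serves both arms, so its error largely cancels in the treatment contrast.

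**Simulation with the SAP's covariates.** The seven-covariate Cox model and five-term logistic model give somewhat larger values:

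- 600 trials per scenario, about 17% vs 8%: no measurable SE change at 6.5% missing. At 12%, B is about 5% too small and the SE 0.1%. At 17%, the figures are 8% and 0.3%. At 25%, of which 17 points are hospitalised losses, they are 14% and about 1% (0.371 vs 0.375; 1 - 0.371/0.375 = 1.1%).
- A separate run at about 16% vs 7%: SE short by under 0.1% at 6% missing, 0.1% at 13%, 0.2% at 20% and 0.7% at 24%. Mean Pe was about 0.08.

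**Type I error at 0.049, both arms 11.5%.** In 8,000 treatment-only trials the fixed method rejected 4.3%, 4.3% and 4.6% at 6%, 12% and 17% missing; the Monte Carlo error is √(0.049×0.951/8000) = 0.24 points. In the 800-trial runs, fixed vs redrawn gave 4.5% vs 4.3% at 6% missing and 5.5% vs 4.8% at 33%, with an error of about 0.8 points.

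**What it could change.** The critical z is 1.969. An SE short by 0.1% alters the decision only for a planned-analysis z between 1.969 and 1.969×1.001 = 1.971, that is p between about 0.0488 and 0.049. At 1% the upper limit is 1.969×1.01 = 1.988, or p of about 0.047.

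**The case against.** The strongest reply is that nothing practical follows. The SAP expects little missing data and counts a last assessment on Days 26-28 as a non-event. Tipping-point analyses vary the event rate among missing subjects from 1% to 40% by arm. Sensitivity analysis 1 removes the discharged draw, and TMLE approach 1 uses neither step. The different handling of sparse post-discharge events is a documented choice (SAP 15.2). All of this stands, and it is why the point is minor. It does not remove it: those analyses test other assumptions and do not correct the variance of the primary analysis. Sensitivity analyses 1 and 2 and TMLE approach 2 keep the fixed Pe, and the FCS sensitivity analysis alters only the PROC MI part.

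Three stronger readings do not hold.

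- **Two of the three groups are always affected.** With 10 or more post-discharge events the discharged group goes to PROC MI, and only the hospitalised or transferred group remains affected.
- **Pe rests on few events.** The Cox model is fitted to all subjects with post-baseline data and uses every observed event. At planning rates that is about 200×0.16 + 200×0.07 = 46. Only the hazard increment after the last assessment depends on later events alone.
- **The SE is short by 1.0% at 13% missing and 2.3% at 18%.** Such figures arise if the Cox step is replaced by Beta draws at an assumed event probability of 0.35. Under the SAP's own step, discharged subjects without an event stay in the risk set, and mean Pe is about 0.08.

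**Conclusion.** The omission is real and visible in the code, and it is a very minor variance error. It always applies to losses while hospitalised or after transfer. It applies to discharged losses only in the expected branch of fewer than 10 events. The between-imputation variance is roughly 5-15% too small. The pooled SE of the log odds ratio is understated by under 0.1% at about 6% missing, about 0.1% at 13%, 0.2-0.4% at 17-20%, and up to about 1% at 24-25% when most losses are in hospital.

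These sizes rest on assumed missingness, discharge timing and post-discharge event rates, because the documents give none. A reader might infer that the primary test is anti-conservative. The simulations show no type I error inflation beyond Monte Carlo error, though the null runs detailed here used treatment-only models. The planned sample size is unaffected.

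**What to change.** Within each of the 20 imputations:

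- **Discharged losses, fewer than 10 events:** draw the rate from Beta(x + 0.5, n - x + 0.5), where x is the number of events among the n discharged subjects with known outcome, and then make the binomial draw. This also covers the zero-event case, where the Beta mean 0.5/(n + 1) is close to the present 0.5/n rule.
- **Hospitalised or transferred losses:** refit the Cox model on a bootstrap sample, or draw its coefficients and baseline hazard, before computing Pe.

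Pooling stays as planned. The cost is a few lines of code and a very slightly wider interval. The Beta mean also sits a little above the raw proportion: in the illustration, 3.5/251 = 1.4% against 1.2%, the same in both arms. If the sponsor prefers to leave the code alone, one sentence in SAP 6.5.1 acknowledging the omitted uncertainty and its expected size would do.
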